8.1.4.3 Secondary Efficacy Variables

Key Secondary Efficacy Endpoints

The following key secondary efficacy endpoints based on data collected during the first 6 months of the treatment period will be summarized by treatment regimen:

- Change from baseline in DYS
- Change from baseline in NMPP
- Change from baseline in dyspareunia
- Change from baseline in Daily Diary endometriosis-associated pain score via NRS
- Change from baseline in rescue analgesic use across both classes of rescue analgesics based on average pill counts
- Percentage of subjects with 30% or more reduction from baseline based on the 35 day mean of the Daily Diary endometriosis-associated pain score via NRS

Additional details regarding the key secondary efficacy endpoints will be provided in the SAP.

Additional Secondary Efficacy Endpoints

Additional secondary efficacy endpoints based on data collected during the first 6 months of the treatment period will include the following.

- Proportion of responders as assessed by change and percent change from Baseline in average pain score and rescue analgesic use monthly for DYS, NMPP, dyspareunia, and Daily Diary endometriosis-associated pain score via NRS, respectively.
- Proportion of responders as assessed by change and percent change from Baseline in average pain score alone (i.e., not taking into consideration of analgesic use) monthly for DYS, NMPP, dyspareunia, and Daily Diary endometriosis-associated pain score via NRS respectively.
- Change and percent change from Baseline, in the monthly average pain score (DYS, NMPP, dyspareunia), and Daily Diary endometriosis-associated pain score via NRS.
- Change from Baseline in rescue analgesic use (average pill counts) to treat endometriosis-related pain, as assessed using information from the e-Diary.
- Proportion of analgesic use responders monthly (based only on reduction of rescue analgesics used).

Additional secondary efficacy endpoints during the 24 months treatment period will include the following.

- Patient Global Impression of Change (PGIC).
- Monthly site administered overall endometriosis-associated pain questionnaire (7-day recall).
- Patient reported outcome (PRO) and outcomes Rating Scales questionnaires.

Summaries for Secondary Efficacy Variables

Unless otherwise specified, no statistical tests will be performed for secondary efficacy endpoints.

Analysis details will be specified in the SAP.

8.1.4.3.1 Dysmenorrhea and Non-Menstrual Pelvic Pain

The proportion of responders, mean change and percent change from baseline to each visit during the first 6 months treatment period in DYS and NMPP will be summarized for each monthly visit.

8.1.4.3.2 Dyspareunia

The proportion of responders, mean change and percent change from baseline to each visit during the first 6 months of the Treatment Period in dyspareunia will be summarized similar to the method for DYS and NMPP.

8.1.4.3.3 Rescue Analgesic Use for Endometriosis-Associated Pain

The use of rescue analgesics for endometriosis-associated pain will be reported by study subjects in the e-Diary during the first 6 months of the Treatment Period.

The rescue analgesic for endometriosis-associated pain taken by the subject will be summarized for the following analgesic categories: (a) NSAID or opioid, (b) opioid and (c) NSAID.

Baseline will be calculated as percentage of days of endometriosis rescue analgesic use for each analgesic category during the last 35 calendar days prior to and including Day 1 during the Screening Period. For the purposes of the rescue analgesic analysis, the number of pills within each class of rescue analgesic (NSAID or opioid) will be considered equivalent, regardless of specific pill choice, e.g., average NSAID pill count will consider all protocol specified NSAIDs specified in [Table 3](#) and will not be conducted separately by NSAID type.

The average pill count for each class of rescue analgesic for each visit during the first 6 months of the treatment period will be calculated by adding the daily pill count of the corresponding class of rescue analgesic in the analysis and dividing over the length of the window, generally equal to 35. For Month 1, average values will be based on data collected between Study Day 1 and the Month 1 reference study day. For Month 4, average values will be based on data collected between Month 3 reference study day and Month 4 reference study day.

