Severe	Severe pain. I had great difficulty doing the things I usually do.

Dyspareunia

Subjects will be asked to assess their dyspareunia (described as 'pain during sexual intercourse'). Subjects will be prompted to "Choose the item that best describes your pain during sexual intercourse during the last 24 hours."

Not applicable	I was not sexually active for reasons other than my endometriosis or did not have sexual intercourse.
None	No discomfort during sexual intercourse.
Mild	I was able to tolerate the discomfort during sexual intercourse.
Moderate	Intercourse was interrupted due to pain.
Severe	I avoided sexual intercourse because of pain.

Uterine Bleeding

Subjects will be prompted to indicate if they had "Did you have any uterine bleeding in the last 24 hours?" For subjects who answer yes, the subject will then document the intensity of the bleeding as follows:

Spotting	A light amount of bleeding noted, no protection or panty shield only.
Light	1 to 2 regular tampons or pads required in 24 hours.
Medium	3 to 4 regular tampons or pads required in 24 hours.
Heavy	More than 4 tampons or pads required in 24 hours.

Daily Diary Endometriosis-Associated Pain Score via Numeric Rating Scale (NRS)

Beginning at Screening, subjects will complete the Daily Diary endometriosis-associated pain score via NRS through Month 6. Subjects will assess in the e-Diary their endometriosis-associated pain during the past 24 hours on a scale of 0 – 10, with 0 = no pain and 10 = worst pain ever.

Rescue Analgesic Use for Endometriosis-Associated Pain

Subjects will record the use of protocol-allowed rescue analgesic medications (Section 5.2.3.4) taken for endometriosis-associated pain on a daily basis using the e-Diary during the Screening Period and through Treatment Month 6. Subjects will report whether they have taken pain medication and document the total number of pills taken within each class (NSAIDs and/or opioids) of protocol-allowed rescue analgesic during the last 24-hour period.

The use of protocol-allowed rescue analgesic medications taken during Treatment Months 7 – 24 will be recorded in the subjects' source documents and eCRF.

Patient Reported Outcomes (PRO) and Outcomes Rating Scales

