8.1.4 Efficacy

8.1.4.1 General Considerations

Analysis details for Months 1 through 24 of the Treatment Period will be specified in the SAP.

The primary efficacy comparisons will be at Treatment Month 6 between the Elagolix 200 mg BID plus E2/NETA treatment group (Group C) and elagolix 150 mg QD group (treatment Group B) in patients who are incomplete responders to elagolix 150 mg QD treatment at Month 3.

For efficacy data collected during Month 7 – 24 of the treatment period, summaries will be provided for the following treatment groups.

- Efficacy responders to elagolix 150 mg QD at Month 3 and continue treatment through Month 24 (Group A).
- Incomplete efficacy responders to elagolix 150 mg QD at Month 3 and randomized to elagolix 200 mg BID plus E2/NETA 1 mg/0.5 mg QD treatment group and continue treatment through Month 24 (Group C).
- Incomplete efficacy responders to elagolix 150 mg QD at Month 3, randomized to elagolix 150 mg QD treatment group and remain incomplete efficacy responders at Month 6, dose increased to elagolix 200 mg BID plus E2/NETA 1 mg/0.5 mg QD through Month 24 (Group D).
- Incomplete efficacy responders to elagolix 150 mg QD at Month 3, randomized to elagolix 150 mg QD treatment group and are efficacy responders at Month 6 continue treatment through Month 24 (Group E).

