8.1.4.2 Primary Efficacy Variable

8.1.4.2.1 Primary Analysis

The primary analysis of the co-primary endpoints will be performed using the Double-blind full analysis set.

The co-primary efficacy endpoints will be the proportion of responders at Month 6 based upon the mutually-exclusive scales for daily assessment of DYS and NMPP measured by the 4 point Endometriosis Daily Pain Impact Diary using the daily e-Diary.

For each of the co-primary endpoints, the criterion for defining a subject as a responder at Month 6 of the Treatment Period will include a reduction of X or greater from baseline in the average pain score as well as no increased analgesic rescue use for endometriosis-associated pain.

The subjects will record use of these rescue analgesic medications on a daily basis in the e-Diary for the first 6 months of the treatment period.

The definition of increased analgesic use is as follows:

- For the primary endpoints of DYS and NMPP, subjects will be considered non-responders if they have a 15% or greater increase from baseline in average pill count of rescue analgesics (endometriosis-associated) as further specified in [Appendix H](#).

For the first 6 months, the rescue analgesic use for any defined period will be based on the average pill count during the analysis window for each class of rescue analgesics: NSAIDs, opioids, and any (NSAIDs and/or opioids). The total pill count for each class of rescue analgesic is the sum of the pill count of the corresponding class of rescue analgesic, as reported in the e-Diary during the time period of interest. For the purposes of the rescue analgesic analysis, the number of pills within each class of rescue analgesic (NSAID or opioid) will be considered equivalent, regardless of specific pill choice,

e.g., average NSAID pill count will consider all types of NSAIDs specified in [Table 3](#) and will not be conducted separately by NSAID type.

For both DYS and NMPP, responses of "None," "Mild," "Moderate," and "Severe" will be assigned a score of 0, 1, 2, and 3, respectively.

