Appendix H. Analgesic Change During Treatment Period

Use of No Analgesics at Baseline		
Analgesic used during Screening	Analgesic dose status at end of study	Responder?*
None	None	Responder
	Opioid analgesic and/or NSAID is started	Nonresponder
Use of Only NSAID at Baseline		
Analgesic used at Baseline	Analgesic dose status at end of study	Responder?*
NSAID	Dose stopped, decreases, or is stable**	Responder
	Dose increases by 15% or more	Nonresponder
	Opioid analgesic is substituted or added	Nonresponder
Use of Only Opioid Analgesic at Baseline		
Analgesic used at Baseline	Analgesic dose status at end of study	Responder?*
Opioid analgesic	Dose stopped, decreases, or is stable**	Responder
	Dose stopped and NSAID substituted (any dose)	Responder
	Dose decreases and NSAID added (any dose)	Responder
	Dose stable** and NSAID added (any dose)	Nonresponder
	Dose increases by 15% or more	Nonresponder
Use of NSAID and Opioid Analgesic at Baseline		
Analgesics used at Baseline	Analgesic dose status at end of study	Responder?*
NSAID + opioid analgesic	NSAID dose stops + opioid analgesic use stops, decreases, or is stable**	Responder
	NSAID use stops + opioid analgesic dose increases by more than 15%	Nonresponder
	NSAID dose decreases + opioid analgesic use stops, decreases, or is stable**	Responder
	NSAID dose decreases + opioid analgesic dose increases by more than 15%	Nonresponder
	NSAID dose stable** + opioid analgesic use stops, decreases, or is stable**	Responder
	NSAID dose stable** + opioid analgesic dose increases by more than 15%	Nonresponder
	NSAID dose increases by more than 15% + opioid analgesic use stops	Responder

Use of NSAID and Opioid Analgesic at Baseline		
Analgesics used at Baseline	Analgesic dose status at end of study	Responder?*
NSAID + opioid analgesic (continued)	NSAID dose increases by more than 15% + opioid analgesic dose decreases	Responder
	NSAID dose increases by more than 15% + opioid analgesic dose is stable**	Nonresponder
	NSAID dose increases by more than 15% + opioid analgesic dose increases by 15% or more	Nonresponder

* Analgesic Responder = Defined as a subject who meets the criteria for no increase in analgesic use.

** Stable = Dose is the same as the baseline dose or increases by less than 15% of the baseline dose.

Assessment of dose is based on number of tablets of NSAIDS/opioids recorded in the Daily e-diary.

Document Approval

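### Rescue analgesic averages: baseline is defined in the wrong unit, and the only pill-count formula counts an unrecorded on-treatment day as zero pills

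*Combined protocol and SAP*

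**What the plan says.** Protocol section 8.1.4.3.3 states the baseline for rescue use: "Baseline will be calculated as percentage of days of endometriosis rescue analgesic use for each analgesic category", taken over the last 35 calendar days up to and including Day 1. For each visit in the first six treatment months it then sums the daily pills in a class and forms the average by "dividing over the length of the window, generally equal to 35". The sentences that follow give shorter calendar windows for Months 1 and 4, which explains why the length is only generally 35. It does not mean the number of diary entries.

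Section 8.1.4.2.1 (primary analysis) says that "the rescue analgesic use for any defined period will be based on the average pill count during the analysis window", and that for DYS and NMPP "subjects will be considered non-responders if they have a 15% or greater increase from baseline in average pill count of rescue analgesics". It refers to Appendix H and gives no divisor. Appendix H adds: "Assessment of dose is based on number of tablets of NSAIDS/opioids recorded in the Daily e-diary". A key secondary endpoint in section 8.1.4.3 is "Change from baseline in rescue analgesic use across both classes of rescue analgesics based on average pill counts".

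On data capture, section 5.3.1.1 says: "Subjects will report whether they have taken pain medication and document the total number of pills taken within each class". On further detail, section 8.1.4.1 says: "Analysis details for Months 1 through 24 of the Treatment Period will be specified in the SAP".

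**The concern.** There are two separate defects.

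**Baseline unit.** Three places need a baseline in pills: the key secondary endpoint, the 15% rule and Appendix H. The one sentence that says how baseline is calculated gives percentage of days. Section 8.1.4.3.3 has no on-treatment percentage-of-days variable to set against it, because its on-treatment measure is the average pill count.

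**Divisor.** With window length as the divisor, an unrecorded day adds nothing to the sum but stays in the denominator, so it is treated as a day without rescue. The diary asks whether any pain medication was taken, so a true zero is a recorded answer and can be told apart from a blank. The plan foresees gaps for the daily NRS, with rules in section 5.1 for subjects who have no NRS entries in the 35-day window. It has no counterpart for pill counts.

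At stake directly are the on-treatment pill-count summaries and the key secondary change from baseline. If the same divisor is carried into the 15% rule, part of the responder definition for both co-primary endpoints would depend on how fully the diary was completed.

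**Working it through.** **1. The plan's own figures.** The plan gives no figure for missing diary days. Its sample-size statements reproduce and are not in dispute. 890 × 0.5 / 2 gives 222 per arm, against 52 per arm needed for 90% power at 20% versus 50%. The 24-month count is 890 × 0.5 × 0.25 + 890 × 0.5 × 0.5 × 0.2 × 0.25 = 111.25 + 11.125 = 122.4, which is at least 120.

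**2. Baseline unit.** Take 1 pill on each of 10 days out of 35 at baseline, and 2 pills on each of 10 days at Month 6.
- Percentage of days: 10/35 = 28.6% both times, a change of 0%.
- Average pill count: 10/35 = 0.286, then 20/35 = 0.571, a change of +100%.

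A change in average pill count therefore cannot be obtained from a percentage-of-days baseline.

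**3. Divisor, complete baseline.** This assumes that the section 8.1.4.3.3 divisor is used in the 15% rule, that use is spread evenly, and that *m* of 35 Month 6 days are unrecorded. A true rise *r* is read as (1 + r)(35 − m)/35 − 1. It escapes the rule when that is below 0.15, that is, when r < 1.15 × 35/(35 − m) − 1.

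| Missing Month 6 days | Rises below this escape the rule | A true +20% is read as |
|---|---|---|
| 1 | 18.4% | +16.6% |
| 2 | 22.0% | +13.1% |
| 5 | 34.2% | +2.9% |
| 9 | 54.8% | −10.9% |

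A rise exactly at the boundary is flagged, because the rule is 15% or greater. With completed days as the divisor, a true +20% is read as +20% in every row, provided that unrecorded days resemble recorded ones.

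**4. Illustrations that add an assumption.** The formula names on-treatment visits only, and no section applies it to baseline. The figures in this step assume that it is used there too.
- Even use, complete Month 6, *b* missing baseline days: stable use is read as 35/(35 − b) − 1. That is +12.9% for b = 4 (passes) and +16.7% for b = 5 (non-responder). At least 45 diary entries are required in Screening (section 5.2.1), so 5 missing days need at least 50 diary days. Screening is 1.5 to 4 months, or 42 to 112 days.
- Intermittent use, by exact enumeration: 2 pills on 10 of 35 days, each day missing independently at the assumed rate. Window length flags a subject if U1 ≥ 1.15 U0. Completed days flags if U1/n1 ≥ 1.15 U0/n0. Here U is recorded use days, n is recorded days, and 0 and 1 denote baseline and Month 6. If U0 = 0, any Month 6 use is flagged. Entries are window length / completed days.

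| Missing at baseline, Month 6 | Stable users flagged (%) | Rises from 10 to 12 days missed (%) |
|---|---|---|
| 5%, 5% | 5.5 / 5.3 | 31.4 / 29.8 |
| 10%, 10% | 12.2 / 13.0 | 40.5 / 37.7 |
| 20%, 20% | 21.7 / 23.3 | 47.1 / 40.9 |
| 10%, 20% | 5.4 / 18.2 | 70.3 / 40.0 |
| 20%, 10% | 37.3 / 20.1 | 20.7 / 40.1 |

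With equal missingness the two divisors differ little for this pattern, by at most about 6 points. For use on 20 of 35 days at 10% in both windows, stable users flagged are 9.0 / 2.6%, and rises from 20 to 24 days missed are 28.4 / 24.6%.

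**The case against.** **The divisor is not stated for the co-primary rule.** Section 8.1.4.3.3 belongs to the secondary variables, which are summarized without tests unless otherwise specified, and section 8.1.4.2.1 points to Appendix H instead. This stands. A reader might infer that the co-primary endpoint is defined with the window-length divisor. The text supports only an inference: same term, same diary, same period and no competing formula.

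**The baseline-gap figures need a second assumption.** This also stands. A reader might infer that stable users will be turned into non-responders by gaps in Screening. No section applies the window divisor to baseline, so step 4 is illustration only.

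**The unit conflict may be a stray sentence.** The co-primary text and Appendix H are worded in pills, and a 15% change in pill count could not be programmed from percentage of days. The conflict is therefore unlikely to change the co-primary result. It remains a direct contradiction in the only sentence that says how baseline is calculated.

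**Details are left to the SAP.** A missing-day rule could be added there, and a final SAP is foreseen before the blind is broken. No separate SAP text is in the document supplied. Deferral can fill a gap, but it does not correct two rules already written down.

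**No harm to the treatment comparison is shown.** A reader might infer bias between arms. Groups B and C are randomized and blinded and share the rule, so bias needs completion to differ between them. Otherwise misclassification mainly dilutes the difference. Even if the highest false-flag rate in step 4 (37.3%) removed responders equally from both arms, 20% and 50% would become 20 × 0.627 = 12.5% and 50 × 0.627 = 31.4%. Power would still be about 99.8% at 222 per arm, or 96% at 133 per arm (890 × 0.6 × 0.5 / 2, assuming 40% loss before Month 3).

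**Conclusion.** Wrong as written, on two counts. The percentage-of-days baseline contradicts the pill-count comparisons elsewhere, and this needs no assumption about missing data. The window-length divisor counts unrecorded on-treatment days as zero pills in the pill-count summaries.

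For the co-primary 15% rule the divisor applies only by inference. On that inference, with a complete baseline and evenly spread use, true rises of up to just under 18.4%, 34.2% and 54.8% pass with 1, 5 and 9 missing Month 6 days.

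The effect has further limits. The pain threshold must also be met. Appendix H rows that turn on any use do not depend on the divisor. Subjects on both classes whose NSAID use rises while the opioid falls or stops stay responders whatever the size of the NSAID rise. Site staff review the diary through Month 6. The documents give no missing-day rate, so the net effect is unknown. Confidence is high for the two wording defects and medium for the carry-over into the co-primary rule.

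**What to change.** In section 8.1.4.3.3, and by reference in section 8.1.4.2.1 and Appendix H:
- Define average pill count per class as total pills reported divided by the number of days in the window with a completed rescue entry. Use it at baseline (the same 35-day window ending on Day 1) and at each month.
- Replace the percentage-of-days baseline with this, and keep percentage of days only as a separate descriptive variable.
- State before unblinding how subjects with no or very few rescue entries in a window are classified, since the divisor is then zero or unstable.
- Report completed rescue days per window by group.

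The cost is a few sentences and some programming. No new data are needed, because the diary already records whether rescue was taken.

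The downside is that the definition assumes unrecorded days resemble recorded ones, so it overstates use if subjects record mainly on pain days. Nor does it lower both error rates in every case. In the step 4 illustrations, with 20% then 10% missing, missed rises go from 20.7% to 40.1% while false flags fall from 37.3% to 20.1%. With 10% then 20% missing, false flags go from 5.4% to 18.2% while missed rises fall from 70.3% to 40.0%. What it removes is the systematic dependence on which window has more gaps; random error from missing days remains.

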8.1.4.3.4 Daily Diary Endometriosis-Associated Pain Score via NRS

The proportion of responders, mean change and percent change from baseline to each visit during the first 6 months treatment period in Daily Diary endometriosis-associated pain score via NRS will be summarized for each monthly visit.

8.1.4.3.5 Additional Endpoints

The additional variables including PGIC, overall endometriosis-associated pain via NRS (11-point NRS, 7-day recall), EHP-30, EQ-5D-5L, WPAI, HCRU, ETSQ and PROMIS Fatigue short Form 6a will be summarized during the 24 months treatment period.

8.1.5 Safety

8.1.5.1 General Considerations

All enrolled subjects who took at least one dose of the study drug will be included in the safety analyses.

Data collected during the 3 month Open-Label Run-In Period will be summarized for all subjects combined.

For safety data collected during Treatment Months 4 – 6, summaries will be presented for the following groups.

- Subjects who are responders to Elagolix 150 mg QD treatment group at Month 3 (Group A) and subjects who are incomplete responders to Elagolix

150 mg QD treatment group at Month 3 and randomized to Elagolix 150 mg QD treatment group at Month 3 (Group B) will be combined

- Subjects who are incomplete responders to Elagolix 150 mg QD treatment group at Month 3 and randomized to Elagolix 200 mg BID plus E2/NETA treatment group at Month 3 (Group C).

For safety data collected during Treatment Months 7 – 24, summaries will be presented for the following group.

- Subjects who are responders to Elagolix 150 mg QD treatment group at Month 3 (Group A) and subjects who are incomplete responders to Elagolix 150 mg QD treatment group at Month 3 and randomized to Elagolix 150 mg QD treatment group at Month 3 and are responders at Month 6 and continue to receive Elagolix 150 mg QD (Group E) will be combined.
- Subjects who are incomplete responders to Elagolix 150 mg QD treatment group at Month 3 and randomized to Elagolix 150 mg QD treatment group at Month 3 and are incomplete responders at Month 6 and are switched to Elagolix 200 mg BID plus E2/NETA (Group D).
- Subjects who are incomplete responders to Elagolix 150 mg QD treatment group at Month 3 and randomized Elagolix 200 mg BID plus E2/NETA treatment group at Month 3 (Group C).

Baseline for all subjects will refer to the data obtained prior to dosing on Day 1 of the Open-label Run-in Period.

In general, for continuous variables, descriptive statistics (mean, standard deviation, median, minimum and maximum) will be summarized by treatment group. Categorical data will be summarized with frequencies and percentages by treatment group. Unless otherwise specified, no statistical tests will be performed.

Analysis details will be specified in the SAP.

